## 6.6 Overview of efficacy analyses

The efficacy analyses are summarized in [Table 4](#).

Each analysis will be accompanied by a summary table with the descriptive statistics.

**Table 4 Summary of efficacy analyses**

Endpoint	Measured by	Analysis	Model	Analysis set	Visits	Data after intercurrent event*
Primary efficacy						
Change from baseline to Week 4 in SiSBP	AOBPM	Main	Mixed model	FAS	Weeks 2,4	Included
		Sensitivity	Multiple imputation (J2R)	FAS	Weeks 2,4	Included
			Multiple imputation (CR)	FAS	Weeks 2,4	Included
			Multiple imputation (tipping point)	FAS	Weeks 2,4	Included
			Mixed model	FAS	Weeks 2,4	Excluded
		Supportive	Mixed model	PPS	Weeks 2,4	NA
			LOCF-ANCOVA	FAS	Weeks 2,4	Included
			BOCF-ANCOVA	FAS	Weeks 2,4	Included
		Subgroup	Mixed model by subgroup	FAS	Weeks 2,4	Included
Key secondary efficacy						
Change from DB-WD baseline (Week 36) to Week 40 in SiSBP	AOBPM	Main	Mixed model	mFAS	Weeks 38,40	Included
		Sensitivity	Multiple imputation (J2R)	mFAS	Weeks 38,40	Included
			Multiple imputation (CR)	mFAS	Weeks 38,40	Included
			Multiple imputation (tipping point)	mFAS	Weeks 38,40	Included
			Mixed model	mFAS	Weeks 38,40	Excluded
		Supportive	Mixed model	mPPS	Weeks 38,40	NA
			LOCF-ANCOVA	mFAS	Weeks 38,40	Included
			BOCF-ANCOVA	mFAS	Weeks 38,40	Included
		Subgroup	Mixed model by subgroup	mFAS	Weeks 38,40	Included

Endpoint	Measured by	Analysis	Model	Analysis set	Visits	Data after intercurrent event*
Other secondary efficacy						
Change from baseline to Week 4 in SiDBP	AOBPM		Mixed model	FAS	Weeks 2,4	Included
Change from baseline to Week 4 in SiDBP	AOBPM		Mixed model	FAS	Weeks 2,4	Excluded
Change from baseline to Week 4 in SiDBP	AOBPM		Mixed model	PPS	Weeks 2,4	NA
Change from baseline to Week 4 in 24 h mean SBP	ABPM		ANCOVA	aFAS	Week 4	Included
Change from baseline to Week 4 in 24 h mean DBP	ABPM		ANCOVA	aFAS	Week 4	Included
Change from DB-WD baseline (Week 36) to Week 40 in SiDBP	AOBPM		Mixed model	mFAS	Weeks 38,40	Included
Change from DB-WD baseline to Week 40 in SiDBP	AOBPM		Mixed model	mFAS	Weeks 38,40	Excluded
Change from DB-WD baseline to Week 40 in SiDBP	AOBPM		Mixed model	mFAS	Weeks 38,40	Included
Change from DB-WD baseline (Week 36) to Week 40 in 24 h mean SBP	ABPM		ANCOVA	maFAS	Week 40	Included
Change from DB-WD baseline (Week 36) to Week 40 in 24 h mean DBP	ABPM		ANCOVA	maFAS	Week 40	Included
Other efficacy						
Change from baseline to Week 4 in mean daytime SBP	ABPM		ANCOVA	aFAS	Week 4	Included
Change from baseline to Week 4 in mean nighttime SBP	ABPM		ANCOVA	aFAS	Week 4	Included
Change from baseline to Week 4 in mean daytime DBP	ABPM		ANCOVA	aFAS	Week 4	Included
Change from baseline to Week 4 in mean nighttime DBP	ABPM		ANCOVA	aFAS	Week 4	Included
Change from DB-WD baseline (Week 36) to Week 38 in SiSBP	AOBPM		Mixed model (key secondary)	mFAS	Weeks 38,40	Included
Changes from DB-WD baseline (Week 36) to Weeks 44 and 48 in SiSBP	AOBPM		Mixed model	mFAS	Weeks 38,40, 44, 48	Included
Changes from DB-WD baseline (Week 36) to Week 38 in SiDBP	AOBPM		Mixed model	mFAS	Weeks 38,40	Included

Endpoint	Measured by	Analysis	Model	Analysis set	Visits	Data after intercurrent event*
Changes from DB-WD baseline (Week 36) to Weeks 44 and 48 in SiDBP	AOBPM		Mixed model	mFAS	Weeks 38,40, 44, 48	Included
Change from DB-WD baseline (Week 36) to Week 40 in mean daytime SBP	ABPM		ANCOVA	maFAS	Week 40	Included
Change from DB-WD baseline (Week 36) to Week 40 in mean nighttime SBP	ABPM		ANCOVA	maFAS	Week 40	Included
Change from DB-WD baseline (Week 36) to Week 40 in mean daytime DBP	ABPM		ANCOVA	maFAS	Week 40	Included
Change from DB-WD baseline (Week 36) to Week 40 in mean nighttime DBP	ABPM		ANCOVA	maFAS	Week 40	Included
Ratio to baseline of UACR			Mixed model	FAS	Week 2 up to Week 36	Included
Ratio to DB-WD baseline (Week 36) of UACR			Mixed model	mFAS	Week 38 up to Week 48	Included
Time from Randomization to discontinuation of study treatment due to lack of efficacy			Cox model (two-step)	FAS	NA	NA
Time from Re-randomization to discontinuation of study treatment due to lack of efficacy			Cox model	mFAS	NA	NA

\* In the DB part: Premature DB treatment discontinuation or addition / dose increase of diuretic (whichever comes first); in the DB-WD part: Premature DB-WD treatment discontinuation, initiation of antihypertensive rescue medication or addition / dose increase of diuretic (whichever comes first).

ABPM = ambulatory blood pressure monitoring; aFAS = ABPM Full analysis set; ANCOVA = analysis of covariance; AOBPM = automated office blood pressure measurement; CR = Copy Reference; DB = double-blind; DBP = diastolic blood pressure; FAS = Full analysis set; J2R = Jump to Reference; LOCF = last observation carried forward; maFAS = modified ABPM Full analysis set; mFAS = modified Full analysis set; mPPS = modified Per-Protocol set; NA = not applicable; PPS = Per-Protocol Set; SiDBP = (mean trough) sitting diastolic blood pressure; SiSBP = (mean trough) sitting systolic blood pressure; UACR = urine albumin-to-creatinine ratio; WD = withdrawal.

## 6.7 Analysis of pharmacokinetic variables

Trough plasma concentrations of aprocitentan are measured at steady state at Week 4. Trough is defined as a sample taken in the morning of the Visit 6 prior to study treatment administration of Visit 6.

Aprocitentan plasma concentrations obtained at Week 4 (Visit 6) will be summarized for the aprocitentan 12.5 mg and 25 mg groups only. Summary statistics include arithmetic mean, SD of the mean, minimum, maximum, median, coefficient of variation (CV%), and number of observations. In these calculations, all values below the limit of quantification will be set to zero. Additionally, summaries will be created by age category, sex, and race.

PK data will be listed for all subjects in the aprocitentan 12.5 mg and 25 mg groups as well as for those subjects in the placebo group that were included as controls.

## 7 SAFETY VARIABLES AND ANALYSES

Safety analyses in the DB and SB aprocitentan parts will be performed on the SAF and rSAF, respectively. Safety analyses in the DB-WD part will be performed on the mSAF.

All safety data will be listed. In the unlikely event that a subject receives DB treatment (or SB aprocitentan treatment, respectively) without being randomized, this subject will not be included in the SAF (or rSAF, respectively), but their safety data will be listed. Similarly, in the unlikely event that a subject received DB-WD treatment without being re-randomized, this subject will not be included in the mSAF, but their safety data will be listed.

### 7.1 Adverse events

#### 7.1.1 Variables

##### 7.1.1.1 Treatment-emergent adverse events

The original terms used by the investigators to describe AEs in the **Adverse Events** eCRF are assigned a PT and a SOC for classification and tabulation using MedDRA (last available version).

Subjects who experienced the same AE more than once within a specified time period (as qualified by the same PT) are counted only once.

An event/assessment is treatment-emergent if the onset/assessment date is between the start date of the randomized treatment period up to EOT+30 days (begin and end dates included). More in particular:

- An event/assessment is DB treatment emergent if the onset/assessment date is between the start date of the DB part up to the day before the start date of the SB treatment part (or EOT + 30 days if the subject did not enter the SB part);

- An event/assessment is SB treatment emergent if the onset/assessment date is between the start date of the SB aprocitentan part up to the day before the start date of the DB-WD treatment part (or EOT + 30 days if the subject did not enter the DB-WD part);
- An event/assessment is DB-WD treatment emergent if the onset/assessment date is between the start date of the DB-WD part up to EOT + 30 days.

An event/assessment with an onset/assessment date between the start date of the run-in period up to the start of randomized treatment period (if the subject is randomized; EOT if the subject is not randomized) will be designated as run-in-emergent.

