 Study treatment including standardized background antihypertensive therapy should be brought back at each visit for drug accountability (pill counts).

 All AEs and SAEs that occur after signing the informed consent form and up to 30 days after study treatment discontinuation must be reported.

 Randomized subjects who prematurely discontinue prior to Week 48/Visit 15 should have an EOT visit scheduled no later than 7 days after the last dose of randomized study treatment.

 For subjects who discontinued during the RI period, this will be a phone call to collect adverse events and concomitant medications only.

ABPM = ambulatory blood pressure monitoring; AE = adverse event; AOBPM = automated office blood pressure measurement; BP = blood pressure; DB = double-blind; ECG = electrocardiogram; EOS = End-of-Study; EOT = End-of-Treatment; FU = follow-up; HR = heart rate; NT-proBNP = N-terminal pro-brain natriuretic peptide; PK = pharmacokinetic(s); RI = run-in; SAE = serious adverse event; SB = single-blind; UACR = urine albumin-to-creatinine ratio; WD = withdrawal.

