### 7.1.2 Analysis

An overview table will be provided displaying by study part (DB, SB aprocitentan or DB-WD) and treatment group (within each study part) the number (%) of subjects with at least one treatment-emergent: AE, SAE, AE leading to premature discontinuation of study treatment, AESI, MACE and MACE-plus (the latter two as confirmed by adjudication).

A similar overview table (but without study part and treatment group) will also be provided for run-in-emergent AEs based on the RIS.

Treatment-emergent AEs will be tabulated by study part (DB, SB aprocitentan or DB-WD), and treatment group (within each study part), SOC and PTs within each SOC: the number and percentage of subjects who experienced at least one AE, at least one AE within each SOC and at least one AE within each PT will be displayed. AEs will also be summarized by decreasing frequency of PT in the aprocitentan 25 mg group.

A similar table (but without study part and treatment group) will also be provided for run-in-emergent AEs based on the RIS.

AEs will also be tabulated by maximum intensity and relationship to aprocitentan or placebo. Relationship to standardized background antihypertensive therapy will only be listed.

If an AE starts in one study part and ends in the next part without increasing intensity, it is counted only in the first part.

Treatment-emergent SAEs will be summarized in a similar manner as AEs.

For EudraCT purposes, non-serious and total death / serious AEs will be summarized separately by study part.

AEs leading to premature discontinuation of study treatment will be summarized in a similar manner as AEs. AESI (except hepatic disorders) will be summarized by CKD stage at Baseline.

The time from Randomization to (first) oedema / fluid retention AESI in the DB or SB aprocitentan part will be summarized by treatment group using Kaplan-Meier plots (supplemented by a table displaying the numbers of subjects at risk, those with an event, and those censored by treatment group, using weekly intervals). For subjects without oedema / fluid retention, the time will be censored at the last dose of DB or SB treatment, whichever comes last. Additionally, a 'two-step' Cox model with a factor for treatment will be fitted [see Section 8.2 for details].

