### 10.1 Analysis periods and visit windows

#### 10.1.1 Analysis periods

The **screening period** is defined as the time from the informed consent date until one day before the run-in period start date (or EOS if the subject does not enter the run-in).

The **RI period** begins at the date of the first dose of RI treatment and ends at the date of the last dose of RI treatment, collected on the **Study Treatment Log** where ‘Study Period’ is ‘Single Blind Run-in’.

The **randomized treatment period** begins at the DB treatment start date and ends at the *last* of the treatment stop dates collected on the **Study Treatment Log** where ‘Study Period’ is not ‘Single Blind Run-in’ and the reason for treatment end is not ‘Interruption due to an AE’ or ‘Interruption not due to an AE’.

The randomized treatment period is divided into three parts: DB, SB aprocitentan and DB-WD.

- The DB part begins at the DB treatment start date and ends at the DB treatment stop date collected on the **Study Treatment Log** where ‘Study Period’ is ‘Double-Blind Treatment (Part 1)’ and the reason for treatment end is not ‘Interruption due to an AE’ or ‘Interruption not due to an AE’.
- The SB aprocitentan part begins at the SB treatment start date and ends at the SB treatment stop date collected on the **Study Treatment Log** where ‘Study Period’ is ‘Single-Blind Treatment (Part 2)’ and the reason for treatment end is not ‘Interruption due to an AE’ or ‘Interruption not due to an AE’.
- The DB-WD part begins at the DB-WD treatment start date and ends at the DB-WD treatment stop date collected on the **Study Treatment Log** where ‘Study Period’ is ‘Double-Blind Withdrawal Treatment (Part 3)’ and the reason for treatment end is not ‘Interruption due to an AE’ or ‘Interruption not due to an AE’.

Should there be any ‘gap’ between the end of one period and the start of the next, then the gap days are allocated to the former period. In the unlikely case that the gap is more than 30 days, gap days 31, 32, etc. will not be allocated to a study part.

The **safety FU period** begins one day after the end of the randomized treatment period and ends at the date of the EOS visit. Safety data obtained during the safety FU period or at the EOS visit will be allocated to the last part of the subject’s randomized treatment period. This is restricted to data collected up to EOT+30 days. Safety data collected beyond that time point will not be allocated to a study part.

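### For subjects never randomised, the run-in AE window closes at EOT although AEs are collected for 30 more days; separately, SAP 7.1.1.1 and 10.1.1 disagree on gaps of more than 30 days between parts

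*SAP*

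**What the plan says.** **Run-in window.** SAP 7.1.1.1 starts the run-in-emergent window at the start of run-in. It closes at the start of randomised treatment for subjects who get that far and at EOT for the others: "if the subject is randomized; EOT if the subject is not randomized) will be designated as run-in-emergent". For randomised subjects the same section defines treatment-emergent as "between the start date of the randomized treatment period up to EOT+30 days (begin and end dates included", and anyone who stops in DB, SB or DB-WD is followed to EOT + 30 days.

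**Collection.** Table 2, footnote 10: "All AEs and SAEs that occur after signing the informed consent form and up to 30 days after study treatment discontinuation must be reported". Footnote 12, on the follow-up contact: "For subjects who discontinued during the RI period, this will be a phone call to collect adverse events and concomitant medications only".

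**Tables.** SAP 7.1.2 plans an overview table of run-in-emergent AEs and a table by SOC and PT: "A similar table (but without study part and treatment group) will also be provided for run-in-emergent AEs based on the RIS". The other AE and SAE tables are by DB, SB and DB-WD, and so is the death table in 7.2.

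**Gaps between parts.** In 7.1.1.1 the DB window runs "up to the day before the start date of the SB treatment part" for subjects who enter SB, and the SB window is built the same way up to DB-WD. Neither has an upper limit. Section 10.1.1 gives the first 30 gap days to the earlier period and then states that "gap days 31, 32, etc. will not be allocated to a study part".

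**The concern.** The run-in tables are the only AE tables open to a subject who was never randomised. If their window is shorter than the collection period, the plan asks sites for safety data that it then leaves out of the tabulated summary. The SAP gives no reason for treating these subjects differently from those who stop in DB, SB or DB-WD.

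The gap rules raise a different problem, because both cannot be programmed. An event, laboratory value or ECG on gap day 31 or later belongs to DB or SB under one section and to no part under the other. What the by-part safety tables show would then depend on which section the programmer followed.

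**Working it through.** The plan states no figure on this point, so the check is a comparison of rules followed by a count of who is affected.

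**1. Does any other rule catch the run-in events?** Take a subject who stops run-in placebo, is not randomised, and has an AE 10 days after EOT.
- Run-in-emergent (7.1.1.1): no, the window closed at EOT.
- Treatment-emergent (7.1.1.1): no, there is no randomised treatment period.
- Safety follow-up period (10.1.1): no, it is defined only as following the randomised treatment period.
- Death table (7.2), if the event is fatal: no, it covers DB, SB and DB-WD only.
- Listings (section 7): yes, all safety data are listed.
- Run-in disposition (5.1.2 and 5.1.3, on the RIS): possibly, if the AE or death is recorded as the reason for stopping.

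Of the 30 collected days after EOT, 0 fall in a tabulated AE window.

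**2. How many subjects?** Inputs from SAP 2.1: about 1500 planned into run-in, at least 600 planned to be randomised, 730 actually randomised. The number who actually entered run-in is not given; 1500 is assumed throughout.
- Planned: 1500 − 600 = 900 subjects (900/1500 = 60%); 900 × 30 = 27,000 subject-days; 27,000/365.25 = 73.9 subject-years.
- With 730 randomised: 1500 − 730 = 770 subjects (51%); 770 × 30 = 23,100 subject-days; 63.2 subject-years.

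Share of all run-in plus follow-up time, under assumed run-in lengths:

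| Assumption | 600 randomised | 730 randomised |
|---|---|---|
| All treated 28 days | 27,000/(42,000 + 27,000) = 39.1% | 23,100/(42,000 + 23,100) = 35.5% |
| Failures treated 14 days, others 28 | 27,000/(29,400 + 27,000) = 47.9% | 23,100/(31,220 + 23,100) = 42.5% |
| All treated 56 days (addendum maximum) | 27,000/(84,000 + 27,000) = 24.3% | 23,100/(84,000 + 23,100) = 21.6% |

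The subject-day totals are upper bounds, because they give every non-randomised subject a full 30 days. The shares also depend on the assumed run-in length. All of these are amounts of follow-up time. None is a count of events.

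**3. Gap rules.** Let the last DB dose be on day 28 and the gap be g days, so SB starts on day 28 + g + 1. Under 7.1.1.1 the DB window ends on day 28 + g. Under 10.1.1 it ends on the earlier of day 28 + g and day 58. Days in conflict = max(0, g − 30).

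| Gap (days) | Days in conflict |
|---|---|
| 0 to 30 | 0 |
| 31 | 1 (day 59) |
| 40 | 10 (days 59–68) |
| 60 | 30 (days 59–88) |

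The same holds between SB and DB-WD.

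**The case against.** **Ending at EOT can be defended.** It keeps the run-in table to time on run-in placebo. Adding 30 days for failures only would give unequal windows within one RIS table, since the window for randomised subjects stops when DB starts. This stands as an argument about presentation, and a separate row answers it. It does not explain why the collected events should be in no AE table.

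**The events are not lost.** This stands. A reader might infer that they appear nowhere but the listings. Run-in disposition can still count an AE or death as a reason, so the claim is limited to AE, SAE and death tables.

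**The size may be smaller.** This stands. Footnote 12 covers subjects who discontinued during run-in, and it is not shown whether the call extends to those who completed run-in and then failed eligibility. Footnote 10 is general. It would be wrong to read 39% as an effect on AE counts, because the documents give no event rate.

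**EOT may be defined elsewhere.** The SAP ties EOT to the randomised treatment period (2.1; Table 2, footnote 11). The full protocol, which is not among the documents supplied, may define it for run-in failures. Whichever date is meant, 7.1.1.1 adds no 30 days to it.

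**Long gaps are rare, and the conflict can be settled either way.** Both stand. A reader might infer that the COVID-19 addendum makes long gaps more likely because Visit 11 may be up to 8 weeks late. The documents do not support this. A late Visit 11 prolongs SB dosing, the addendum (2.1.1, 2.1.2) makes rescheduling conditional on sufficient medication and arranges resupply, and 10.1.1 does not treat a logged interruption as the end of a part. Nor should the omitted run-in events be described as arising after background therapy was stopped; nothing supplied says that it was.

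**Conclusion.** Both points hold, and both are minor.

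First, the run-in window for subjects never randomised omits 30 days of collected AE follow-up from every AE, SAE and death table. This affects up to about 900 subjects by plan, or about 770 with 730 randomised and an assumed 1500 in run-in. The number of events omitted cannot be estimated from the documents. The consequence is incomplete run-in safety reporting. The efficacy tests, alpha and the DB comparison with placebo are unaffected.

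Second, 7.1.1.1 and 10.1.1 contradict each other once a gap exceeds 30 days. The number of such gaps is not given. Where one occurs, off-drug events may be charged to the earlier part, which is aprocitentan 25 mg in SB, or left out of the by-part tables.

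**What to change.** **Run-in.** Define EOT for a subject who is never randomised, and change 7.1.1.1 so that this subject's run-in-emergent window ends at EOT + 30 days. Preferably show the post-placebo days in a separate row, so that the on-placebo count stays comparable across the RIS. Because 7.2 has no run-in category, also add one there or state where run-in deaths are counted. The cost is one extra row and slightly higher run-in counts; no new data are needed.

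**Gaps.** Use one rule in both sections. Either option works:
- Cap the DB and SB windows in 7.1.1.1 at the last dose of that part + 30 days. Events after the cap would still be treatment-emergent overall but would have no part, so the SAP must also say where they are reported.
- Drop the cap in 10.1.1 for safety data, so that every treatment-emergent event keeps a part. The price is that some events long after the last dose are attributed to it.

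Either way the cost is a sentence or two in the SAP.

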#### ***7.1.1.2 Relationship of treatment-emergent adverse events***

Relationship to study treatment, standardized background antihypertensive therapy and study design or protocol-mandated procedures is determined by the investigator as 'Unrelated' or 'Related' **Adverse Events eCRF**. If (even after repeated querying) the relationship is missing, the event is considered 'Related'.

#### ***7.1.1.3 Intensity of treatment-emergent adverse events***

The intensity of an AE is determined by the investigator as 'mild', 'moderate' or 'severe' on the **Adverse Events eCRF**. If an AE increases in severity this will be collected in a separate record with a new onset date (including a link to the record with the lower intensity; both AEs are considered treatment-emergent and will be analyzed as such). Subjects who experienced the same AE more than once within a specified period/part (as qualified by the same PT) but with different intensities are counted only once, using the worst reported intensity. If (even after repeated querying) the intensity is missing, the event is considered severe.

#### ***7.1.1.4 Serious adverse events***

An SAE is defined as an AE where 'Serious' is 'Yes' the **Adverse Events eCRF**.

#### ***7.1.1.5 Adverse events leading to discontinuation of study treatment***

These are AEs where 'Action taken with study treatment (aprocitentan or placebo)' is 'Permanently discontinued' on the **Adverse Events eCRF**.

Notes: AEs starting in the RI period, but leading to discontinuation of study treatment in the randomized treatment period will be counted in the latter period; AEs leading to discontinuation of standardized background antihypertensive therapy are not counted.

